1.4.3 Rationale for Combination of Y90-RE and Durvalumab

While surgery remains the conventional definitive treatment for metastatic liver cancer, many patients are unamenable at presentation and most will ultimately sustain disease recurrence. (Vigano, et al, 2013; Cucchetti, et al, 2009) The inherent limitations of traditional staging with serologic, imaging, and histologic assessment lack the sensitivity to detect microscopic disease in its entirety outside of the treatment field. Theoretically, extirpation of metastatic disease may remove tumor antigens that, if properly exploited, could potentially generate signal for comprehensive immune mediated disease control. For patients with surgically unmanageable disease, locoregional treatments that maximize antigenic exposure may produce

immunologic responses that could provide a powerful adjunct to therapy while maintaining quality of life with a minimally invasive, outpatient, procedure.

Sustained immune tumoricidal responses require complex environmental interactions of antigen recognition and presentation, T cell activation, T cell relevance in the setting of continuous tumor genetic variation, and circumvention of tumor suppression mechanisms. The locoregional modalities which have shown particular promise in preserving tumor antigen allowing for host activation include cryoablation, irreversible electroporation, ischemic therapies such as embolization, and vascular micro-brachytherapy achieved via transarterial radioembolization. A large body of literature has been already generated to support ionizing radiation as an immunologic adjuvant to many of these requirements. (Kang, et al, 2016)

Localized radiation therapy holds great promise as an immunologic antitumor adjuvant. Radioembolization has a wide range of exclusive properties that warrant exploration to determine how best to incorporate it within the radiotherapeutic inventory. Given an increasing knowledge base and experience with radioembolization, and the current enthusiasm for immunotherapy-based oncology, currently recruiting clinical trials will hopefully materialize the promise of their synergism.

The clinical benefit of using Y90-RE in combination with durvalumab is yet to be known since immunotherapy has not, to date, significantly benefited patients with mCRC. However, addition of Y90-RE may improve the antigen exposure to immunotherapy and further improve the outcome of the treatment.

Furthermore, both Y90-RE and durvalumab will be used at the dose recommended by the manufacturer in which the doses are well established. Given the absence of any significant untoward side effects, major safety issue is not expected and there is potential benefit. Concurrent translational and correlative data would significantly improve insights on how to help improve immunotherapy as an option for patients with mCRC.

1.4.5 Rationale for Durvalumab Dose Escalation

The trial, for each subject, will consist of a screening period, a treatment and observation phase. The treatment phase is approximately 2 months with Y90-RE in combination with fixed dose durvalumab and **the dose limiting toxicity (DLT) observation phase for 8 weeks post Y90-RE**. The rationale for the proposed dosing schema is keeping in mind the timing of toxicities that are typically seen post Y90-RE. Most patients have elevation of their liver enzymes the first 1-2 weeks. Therefore, with the dosing escalation, we did not include the added dose at week 2 for the first dose escalation (see dose level table – section 7.41 and Table 1 section 1.23 below). Patients get fixed dosing of immunotherapy, which is the case for all immunotherapy-based studies. Depending on the dose level, patients can get a maximum of 2 doses before and 3 doses post Y90-RE. As noted in Table 1 (section 1.23 below), while dose level 1 and dose level -1 have the same number of durvalumab administrations, they are different since dose level 1 get 2 doses pre-Y90-RE ('priming doses of immunotherapy before Y90-RE) while dose level -1 only get 2 doses post-Y90-RE.

1.4.6 Study Design

This clinical trial will be conducted as a single-center, open-label, Phase I trial to evaluate the feasibility and safety of Y90-RE in combination with a fixed dose of durvalumab in subjects with liver-predominant, mCRC. It can be offered in the refractory setting and/or more so integrated into the current standard systemic chemotherapy ± biologics, by focusing on enhancing the effect of Y90-RE with immunotherapy. Therefore, there is the option for patients with significant liver-predominant disease burden that are considered candidates for Y90-RE to temporarily discontinue their current chemotherapy in order to participate within this trial. Subjects will be approached for screening at outpatient clinic visit appointments and interested qualified subjects will be consented and offered participation in this trial. Once consent has been obtained, for eligible subjects, baseline values will be established, and subjects will begin treatment and be followed-up for the next three months. The washout period to begin treatment (cycle 1 day 1) for

this clinical trial will be at least 2 weeks after prior chemotherapy or biologic. Screening can begin prior. The goal is to keep the duration on the clinical trial minimal.

The trial, for each subject, will consist of a screening period, a treatment and observation phase. The treatment phase is approximately 2 months post-Y90-RE in combination with fixed dose durvalumab. The DLT observation phase will be for 8 weeks post dose of Y90-RE.

The trial will be performed in **18 subjects** with mCRC with liver metastasis and the safety of immunotherapy (durvalumab) with Y90-RE will be investigated in an accelerated titration design. This would allow a maximum tolerated dose with the minimum number of subjects. At any point as noted below if there is a DLT, the study design defaults to a standard 3+3 design. Assuming a 10% loss of subjects after enrollment, the dose escalation design will require at least 9 evaluable subjects to establish the highest dose level as the maximum tolerated dose (MTD). If less than 18 subjects are administrated in the dose escalation, the rest of subjects will be administrated the MTD in the expansion cohort. **Sample size of maximum of 18 was based on an accelerated titration design and on the correlative studies including pre- and post-biopsies. The primary goal of this study is to establish safety and with a secondary goal of looking at biomarkers and other immune signals as noted.**

This study will utilize an accelerated titration design. The dose levels to which patients will be assigned in sequential cohorts are listed in the table 1.

Table 1. Dose escalation cohort of durvalumab*

		Immunotherapy (Durvalumab) Administrations						Number of Administration of Durvalumab	
Dose level	Pre-Y90 doses		Post-Y90 doses			Week2	Week4	Week6	
	Week-2	Week0	Week2	Week4	Week6				
-2					X				1
-1				X	X				2
1 (start)**	X	X							2
2	X	X		X					3
3	X	X		X	X				4
4	X	X	X	X	X				5

* Please note: As noted above, the rationale for the proposed dosing schema is keeping in mind the timing of toxicities that are typically seen post Y90-RE. Most patients have elevation of their liver enzymes the first 1-2 weeks. Therefore, with the dosing escalation, we did not include the added dose at week 2 for the first dose escalation (dose level 2). Patients get fixed dosing of immunotherapy, which is the case for all immunotherapy-based studies. Depending on the dose level, patients can get a maximum of 2 doses before and 3 doses post Y90-RE (dose level 4).

**While dose level 1 and dose level -1 have the same number of durvalumab administrations, they are different since dose level 1 get 2 doses pre-Y90-RE ('priming doses of immunotherapy before Y90-RE) while dose level -1 only get 2 doses post-Y90-RE.

A single patient will be treated per dose level until the first DLT is recorded. Once the first DLT is recorded, two additional patients are treated at the same dose level and the trial reverts to a standard 3+3 design. At which time, decisions on when and how to dose escalate are described below.

Number of patients with DLT at a given dose level	Decision Rule
0 out of 3	Enter 3 patients at the next higher dose level
1 out of 3	Enter up to 3 additional patients at the same dose level. 
 • If 0 of these 3 patients experience DLT, proceed to the next dose level. • If 1 or more of these 3 patients experience DLT, then dose escalation is stopped, and this dose is declared the maximally administered dose. Three (3) additional patients will be entered at the next lowest dose level if only 3 patients were treated previously at that dose.
≥ 2 out of 3	Dose escalation will be stopped. This dose level will be declared the maximally administered dose. Three (3) additional patients will be entered at the next lowest dose level if only 3 patients were treated previously at that dose.

Up to 6 patients will be treated at each dose level. The MTD will be defined as the highest dose level for which at most 1 out of 6 patients experience a DLT. If DLT meets the stopping boundaries set by the above dose algorithm at dose level 1 (for example, more than 1 out of 3 or more than 1 out of 6 patients), the next cohort of 3 patients will be entered at the dose level of -1. If dose level -1 meets the stopping boundaries, the next cohort of 3 patients will be entered at dose level -2.

If an MTD is determined, an expansion cohort using the RP2D will be carried out in additional patients for a maximum of 18 patients. If an MTD is not determined, the expansion cohort will utilize the dosing scheme from cohort 4.

After the end of treatment visit (EoT) subjects (if applicable) are to resume the previously discontinued chemotherapy until all cycles have been administered or treatment is discontinued as per regular standard of care or secondary resection if deemed a candidate. The decision to resume the previously discontinued chemotherapy is to be done at investigators discretion. As the patients will commence a different treatment regime, no active follow-up will be done as part of this study other than progression free survival and overall survival.

The clinical trial will be conducted at one site, the Holden Comprehensive Cancer Center, University of Iowa.

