1.4.7 Number of Subjects

This clinical trial will recruit 18 subjects. The estimated recruitment rate is at least one subject every 1-2 months, in which a minimum of 12-18 subjects will be enrolled over a period of 18-24 months. The number of subjects in the dose escalation will depend on the number of dose levels needed to determine the MTD or confirm the current dosing for durvalumab can be used in combination with Y90-RE. **The dose limiting toxicity (DLT) observation phase is 8 weeks post Y90-RE.**

In the expansion cohort, the remaining subjects (from the total 18 subjects) will be treated at the MTD dose of the combination of Y90-RE and durvalumab. Since all patients received immunotherapy and Y90-RE, they would be included in the evaluation of efficacy objectives and correlative components of the study.

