17.0 Statistical Considerations and Methodology

17.1 Study Design

This is a single arm phase I study designed to determine the maximally tolerated dose (MTD) and toxicity profile of Yttrium-90 radioembolization combined with immunotherapy in the treatment of liver-predominant, metastatic colorectal cancer using the accelerated titration design.

Once the MTD is reached, if total accrual is less than 18, additional patients will be enrolled in an expansion cohort to reach full accrual of 18 patients.

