Up to 6 patients will be treated at each dose level. If DLT meets the stopping boundaries set by the above dose algorithm at dose level 1 (for example, more than 1 out of 3 or more than 1 out of 6 patients), the next cohort of 3 patients will be entered at the dose level of -1. If dose level -1 meets the stopping boundaries, the next cohort of 3 patients will be entered at dose level -2.

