17.3 Sample Size

This phase I study is expected to require 9 evaluable patients to establish the highest dose level as the MTD. We do not expect serious adverse events or DLTs based on experience of treating patients with Y90-RE. Experience with immunotherapy as well has been reassuring from a safety perspective. Anecdotally, we have had some patients who were on immunotherapy for HCC, which got FDA approved in October 2017 who got Y90-RE with no untoward side effects and good responses. Given the clinical experience and data that is available so far, we do not expect to reach the maximum accrual dictated by budget restrictions during the MTD determination portion of the study. Once the MTD is determined, additional patients will be accrued in an expansion cohort in order to reach full accrual of 18 patients between Phase I and the expansion cohort.

The primary objective of the expansion cohort is to evaluate whether Y90-RE in combination with durvalumab confers an immune response (mechanism of action) irrespective of dose level as estimated by the change in frequency of immune cells pre- and post-treatment. A sample size of 18 patients will allow the sample mean for the pairwise difference to be estimated with a 95% confidence interval half-width of 0.5 SD.

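### The level 4 fallback for the expansion cohort in section 1.4.6 is not limited to trials in which no dose level has met the stopping boundary

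*Combined protocol and SAP*

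**What the plan says.** Sections 1.4.6 and 17.2 treat one patient per level until the first DLT, then add two at that level and continue as 3+3. With two or more DLTs in three, the table in 1.4.6 says: "Dose escalation will be stopped. This dose level will be declared the maximally administered dose". One DLT in three followed by any DLT in the next three has the same effect. Either way, three more patients go to the level below, on condition that three were treated there before. The MTD is the highest level with at most one DLT in six patients.

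The step-down ladder runs from level 1 to -1 to -2. Its last rung, the same in both sections, is: "If dose level -1 meets the stopping boundaries, the next cohort of 3 patients will be entered at dose level -2". Nothing follows on what happens if level -2 stops.

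On the expansion cohort:
- 1.4.6, after the table: "If an MTD is not determined, the expansion cohort will utilize the dosing scheme from cohort 4". Level 4 is the five-dose scheme; level -2 is one dose.
- 1.4.6, before the table: "the rest of subjects will be administrated the MTD in the expansion cohort".
- 1.4.7: "the remaining subjects (from the total 18 subjects) will be treated at the MTD dose".
- 17.1: "Once the MTD is reached, if total accrual is less than 18, additional patients will be enrolled in an expansion cohort".
- 17.3: "Once the MTD is determined, additional patients will be accrued in an expansion cohort".

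Footnote 17 in section 4.1 attaches the five-dose schedule to the expansion cohort without any condition.

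**The concern.** A fallback that names the highest exposure should apply only when nothing has gone wrong below it. This one is triggered by the absence of an MTD, and an MTD can be absent because a lower exposure proved too toxic. In that situation one dosing sentence points to five durvalumab doses, others imply that there is no expansion, and no sentence in the pages shown closes accrual. This is the first trial of the combination and its primary goal is feasibility and safety, so the rule for the worst path should not need interpretation.

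**Working it through.** **1. The plan's own figures reproduce.** Nine evaluable patients to establish the top level as MTD: 1 + 1 + 1 at levels 1 to 3 plus 6 at level 4 = 9. Half-width of 0.5 SD with 18 patients: t(0.975, 17)/√18 = 2.110/4.243 = 0.497.

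**2. When is no MTD determined?** A level 4 with at most one DLT in six is itself the MTD, so that case does not need the fallback. What remains, apart from reaching the 18-patient cap (no places left):
- Level 4 is reached, no level has stopped, but level 4 holds fewer than six patients. This is the likely intended case.
- (a) Levels 1, -1 and -2 all stop. The table stops escalation, but its next step needs a lower level and none exists.
- (b) The first DLT occurs at level 2, 3 or 4 and that level stops. The level below holds one patient. The table's condition is that three were treated there, so read literally nobody is added. Even if three were added, the level would hold 1 + 3 = 4, not six.

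**3. Places left of 18.** Case (a): each level uses 3 or 6 patients, so 9, 12, 15 or 18 are used and 9, 6, 3 or 0 remain. Case (b): if level 2 stops, 1 + 3 = 4 or 1 + 6 = 7 are used; level 3, 5 or 8; level 4, 6 or 9. So 9 to 14 remain.

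**4. Probability of case (a), direct path.** The documents give no DLT rate, so p is assumed; q = 1 − p.
- Level 1, first patient has a DLT: stop with 3 = p(1 − q²); stop with 6 = pq²(1 − q³).
- Levels -1 and -2: stop with 3 = 1 − q³ − 3pq²; stop with 6 = 3pq²(1 − q³).

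At p = 0.3: level 1 gives 0.1530 + 0.0966 = 0.2496; each lower level gives 0.2160 + 0.2897 = 0.5057. All three stop: 0.2496 × 0.5057² = 0.0638. All 18 used: 0.0966 × 0.2897² = 0.0081. Places left: 0.0638 − 0.0081 = 0.0557.

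| Assumed DLT rate at levels 1 / -1 / -2 | All three stop | With places left |
|---|---|---|
| 0.2 / 0.2 / 0.2 | 0.0114 | 0.0092 |
| 0.3 / 0.3 / 0.3 | 0.0638 | 0.0557 |
| 0.4 / 0.4 / 0.4 | 0.1760 | 0.1630 |
| 0.3 / 0.2 / 0.1 | 0.0068 | 0.0056 |
| 0.4 / 0.3 / 0.2 | 0.0544 | 0.0482 |
| 0.5 / 0.4 / 0.3 | 0.1692 | 0.1585 |

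Given places left, the mean number is 4.6, 5.0 and 5.6 at equal rates 0.2, 0.3 and 0.4. The nine-place case has probability 0.08%, 0.7% and 3.2%.

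**5. Probability of reaching the position in case (b).** The first-DLT level stops with probability p(1 − q²) + pq²(1 − q³) = p(1 − q⁵). It is level 2, 3 or 4 after one, two or three DLT-free single patients, so the total is (q + q² + q³) × p(1 − q⁵). At equal rates:
- 0.2: 1.952 × 0.1345 = 0.26
- 0.3: 1.533 × 0.2496 = 0.38
- 0.4: 1.176 × 0.3689 = 0.43

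This is the chance of arriving where the table fails, not the chance that anyone is given five doses.

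**6. Comparison.** Four single DLT-free patients: q⁴ = 0.41, 0.24 and 0.13 at the same rates. This omits routes that reach level 4 after a DLT that does not stop escalation.

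**The case against.** The best defence is that the sentence sets the dose of an expansion cohort and does not open one. Opening is governed by 17.1 and 17.3, which wait for an MTD. Naming cohort 4 fits a trial that got there. Section 1.4.7 offers, as the alternative to finding the MTD, that the trial may "confirm the current dosing for durvalumab can be used in combination with Y90-RE", and 17.3 expects no DLTs. The table applies at every level, including -2, and going from one dose to five would be escalation, which it stops. The supporting conflicts are also uneven: the direct tension is with the earlier sentence of 1.4.6 and with 1.4.7; with 17.1 and 17.3 it arises only by omission. Footnote 17 is a schedule label, not a decision rule.

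Oversight would very probably intervene. Case (a) needs at least six DLTs, two at each of three levels. Each goes to the Study Chair as soon as it occurs (7.4.1.2) and into a report within 1 business day (10.5.5), and 17.2 requires 8 weeks of observation after Y90-RE before new patients are treated. Section 10.5 mentions study stopping rules, and section 10 a detailed monitoring plan on file that is not shown; a closure rule may be there.

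All of this stands, and it limits the point to a defect of wording. It does not supply the missing condition, and it does not repair the table in case (b).

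**Conclusion.** The fallback is worded too broadly, and the rules around it leave two gaps: nothing after level -2 stops, and no workable step when a level stops above a single-patient level. It merits a safety clarification, between minor and should-fix.

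A reader might infer that the protocol orders five doses after one- and two-dose schedules have failed. The documents do not support that: the text conflicts with itself, and the likely intent is benign. Nor can one say that case (a) is likely. It is uncommon unless toxicity is high even at one or two doses, and the 16% figures need 40% at every level or 50/40/30%. Case (b) would be reached often at these rates, but investigators would most likely add patients at the lower level; the five-dose outcome requires applying both sentences to the letter.

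All probabilities assume independent patients and the stated rates. Case (a) counts only the direct descent from level 1, and case (b) assumes the same rate at levels 1 to 4.

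**What to change.** 1. Replace the fallback sentence in 1.4.6 with: *When level 4 is reached and no level has met the stopping boundary, level 4 is filled to 6 patients under the 3+3 boundary as part of MTD determination. If at most 1 of the 6 has a DLT, level 4 is the MTD and the expansion cohort uses it. No patient enters at or above a level that has met the stopping boundary.*
2. Add to 1.4.6 and 17.2: *If level -2 meets the stopping boundary, accrual stops and no expansion cohort opens.*
3. In both decision tables, make the step-down condition that fewer than six patients have been treated at the lower level, and fill it to a total of six.
4. Relabel footnote 17 in 4.1 as dose level 4, and the expansion cohort if level 4 is the MTD.

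Sections 17.1 and 17.3 can stay, because every expansion then follows an MTD. The DLT-free route is unchanged: 3 single patients plus 6 at level 4 = 9, then up to 9 more.

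Costs: in case (a) the trial ends at 9, 12 or 15 patients, and the half-width for the paired immune change, t(0.975, n − 1)/√n, is about 0.77, 0.64 or 0.55 SD instead of 0.5 SD. In case (b), filling a one-patient level takes 5 of the remaining places. If levels 4 and 3 both stopped, this could need 9 + 5 + 5 = 19 patients, above the cap of 18, so the trial could end without an MTD.

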1.4.7 Number of Subjects

This clinical trial will recruit 18 subjects. The estimated recruitment rate is at least one subject every 1-2 months, in which a minimum of 12-18 subjects will be enrolled over a period of 18-24 months. The number of subjects in the dose escalation will depend on the number of dose levels needed to determine the MTD or confirm the current dosing for durvalumab can be used in combination with Y90-RE. **The dose limiting toxicity (DLT) observation phase is 8 weeks post Y90-RE.**

In the expansion cohort, the remaining subjects (from the total 18 subjects) will be treated at the MTD dose of the combination of Y90-RE and durvalumab. Since all patients received immunotherapy and Y90-RE, they would be included in the evaluation of efficacy objectives and correlative components of the study.

1.4.8 Duration of Participation

The total duration of the trial for each subject will be approximately three months (from the first subject first visit to first subject last observation). The entire trial from the first subject enrollment to the last subject visit (end of treatment visit) will last 24 months. For the purpose of data analysis, the trial will start with first subject signing informed consent and will end when the last subject performed the last clinical follow up visit, under the standard protocol. After the last clinical follow up visit, planned time needed for final report/publication following last subject last visit is six months.

1.3 Correlative Research

- Immune Correlates (Pre- and Post- immunotherapy and Y90-RE)
- Tumor Correlates (Pre- and Post- immunotherapy and Y90-RE)

The specifics and timing of sample collection are detailed in the schedule of testing/**companion laboratory manual** for this clinical trial. Both in-house research/clinical as well as commercially available platforms would be utilized to accomplish the goals listed.

Broadly speaking as noted, the main goal would be study 2 main correlates (pre- and post- Y90-RE and immunotherapy) from a) an immune perspective and b) tumor perspective. As noted in detail in the schedule of testing and companion laboratory manual, there are additional serial collections from a blood testing perspective to allow for assessment of blood-based immune markers as well as tumor based liquid biopsies (circulating tumor DNA testing – ctDNA testing).

[figure not shown]
1.3.1 Immune correlates:

Analysis of immune cells by flow cytometry: Analysis of immune cell populations via flow cytometry will allow for more quantitative and in-depth profiling of immune cells. In addition, these experiments will be done at the University of Iowa at the time of sample collection.

Immune cell analysis of peripheral blood and tumor tissue: Frequencies of innate (monocytes, macrophages, neutrophils, dendritic cells, NK cells) and adaptive (CD4+ T cells, CD8+ T cells, NKT cells, B cells) immune cells present in the peripheral blood or tumors of patients will be determined via flow cytometry. In addition, we will examine expression of inhibitory markers on T cells including, but not limited to, PD-1, CTLA-4, TIM3 and LAG3. For peripheral blood samples we will compare frequencies of immune cell populations at the several serial time points as denoted in the table. Tumor infiltrating cells in tumor tissue samples will be compared at two time points for the tissue as denoted in the schedule of testing/companion laboratory manual.

Serum cytokine and chemokine analysis: Use of a Multiplex assay will allow us to examine multiple cytokine and chemokine targets at multiple time points with use of minimal serum sample. These again would be done at the University of Iowa at the time of sample collection. Serum will be collected from peripheral blood of patients at 8 different time points as denoted in the table. A bead based multiplex assay will be used to quantitatively measure levels of 27 different cytokines and chemokines at various time points. This analysis will be done at the University of Iowa.

From a tumor microenvironment perspective, would evaluate for immune related changes including PD-L1 and PD-1 expression and tumor-infiltrating lymphocytes.

1.3.2 Tumor correlates:

We will have 2 timepoints of tumor evaluation in terms of tissue i.e. pre- and post-immunotherapy and Y90-RE. Additionally, a unique and strong aspect of this study is the use of **liquid biopsies** (ctDNA/circulating tumor DNA testing) at multiple serial timepoints.

- We will measure the variant allele fraction (%) and the spectrum of mutations through next generation sequencing based platforms.
- Tumor mutation burden would also be estimated and studied.
- On tissue whole exome sequencing would be performed pre- and post-immunotherapy and Y90-RE.
- Gain and/or loss of clones and sub-clones would be studied serially on liquid biopsies.

Details of the tissue and immune based collection including specimen and handling requirements outlined in details in schedule of testing/**companion laboratory manual** for this clinical trial.

Of note, if enough tissue is available and lesions are safe/amenable to biopsy, feasibility of developing patient derived organoids, xenografts and cell-lines at the time of pre- and post-treatment biopsies will be evaluated.

Additional Correlates:

- For patients where we have stool and swab samples available, we would run panel-based microbiome profile inhouse with [name] lab. Initially the specimens would be biobanked.
- Where tissue is sufficient, would assess the feasibility of developing a cell line and/or organoid for drug testing. However, the tissue correlates outlined earlier take priority first.

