The overarching goal of the expansion cohort is to gain preliminary evidence as to whether Y90-RE in combination with durvalumab confers an immune response, the hypothesized mechanism of action. Immune response will be assessed by estimating the mean change in the frequencies of immune cells from pre-treatment to post-treatment. More specifically, each patient's immune cell frequencies at pre-treatment will be subtracted from the post-treatment value to obtain the pairwise difference for a patient. Immune cell analysis will include, but is not limited to, the frequencies of innate (monocytes, macrophages, neutrophils, dendritic cells, NK cells) and adaptive (CD4+ T cells, CD8+ T cells, NKT cells, B cells) immune cells. A change in immune cell frequencies after treatment is anticipated, but the expected average change for each type of immune cell is not known, thus the purpose of the expansion cohort. No formal hypotheses are being tested, rather the change in immune profile along with other data obtained (e.g. changes in circulating tumor DNA, tumor response to treatment, etc.) will be collectively evaluated and used to inform a subsequent Phase II trial. From previously done similar studies, a 25% change is taken to represent a biologically meaningful downregulation of some of the key negative players (e.g. Tregs) and upregulation of positive players (e.g. PD-L1) expression, which will be taken into consideration when evaluating the immune profile.

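### Running the serum cytokine assay at each visit, as Section 1.3.1 states, puts avoidable between-run error into every within-patient change in this exploratory correlate

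*Combined protocol and SAP*

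**What the plan says.** Section 1.3.1 (Immune correlates) describes two assays. Of flow cytometry it says "these experiments will be done at the University of Iowa at the time of sample collection". The paragraph on serum cytokines and chemokines repeats the arrangement: "These again would be done at the University of Iowa at the time of sample collection". It continues: "Serum will be collected from peripheral blood of patients at 8 different time points as denoted in the table", and "A bead based multiplex assay will be used to quantitatively measure levels of 27 different cytokines and chemokines at various time points". Section 1.3 presents the immune correlates as pre- and post-treatment comparisons.

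Section 17.3 gives the only stated precision for a pre/post change: with 18 patients, the mean change is expected to have a "95% confidence interval half-width of 0.5 SD". The change it refers to is defined for cells: "immune cell frequencies at pre-treatment will be subtracted from the post-treatment value to obtain the pairwise difference for a patient". Section 17.3 adds that other data will be considered together with the immune profile to inform a phase II trial.

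Cytokines are not named in Section 17.3, in the correlative goals (2.3) or in Laboratory Correlates (17.5.6). Sections 1.3 and 14.0 refer specimen handling to a companion laboratory manual, which is not among the documents. Nothing in the documents provides for batching a patient's serum samples, a control shared between runs, control of reagent lots, or a run term in the analysis.

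**The concern.** A pre/post change is cleanest when both samples go through the same run, because whatever is peculiar to that run is common to both and cancels. Assaying at collection gives up that cancellation. Each change then carries the error of two separate runs. Anything that shifts the assay between the two dates, such as instrument drift or a new reagent lot, appears as a change in the patient. The trial has a single arm, so no concurrent untreated group would show the same shift.

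Nothing in the protocol needs the result early. The DLT definitions (7.4.2), the dose modification table (8.21) and the escalation rules (17.2) use no cytokine value. At stake is how readable one exploratory correlate will be when the immune findings are considered together.

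**Working it through.** **Time between paired samples.** The Section 17.2 table puts the first durvalumab dose at week -2. Footnote 12 of Section 4.1 puts the end-of-treatment visit 8 weeks after Y90-RE. The gap is 2 + 8 = 10 weeks, apart from visit windows, and longer if the screening draw is taken as baseline.

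**The plan's own figure.** For the mean of n = 18 paired differences, half-width / SD = t(0.975, 17) / √18 = 2.110 / 4.243 = 0.497. The stated 0.5 SD is reproduced. It is for immune cell frequencies. It is also in units of the observed SD, so it would stay at 0.497 whatever the assay error. Assay error enlarges the SD itself.

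**Effect of separate runs.** Let s be the SD of the true relative change and c the between-run CV. Neither is in the documents, so both are assumed.

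- Same run: the run effect cancels and the variance of the change is s².
- Separate runs: the variance is s² + 2c².
- Growth in SD, and in interval width at any fixed number of patients: √(1 + 2c²/s²).

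| s | c = 10% | c = 15% | c = 20% |
|---|---|---|---|
| 25% | √1.32 = 1.149 | √1.72 = 1.311 | √2.28 = 1.510 |
| 50% | √1.08 = 1.039 | √1.18 = 1.086 | √1.32 = 1.149 |
| 80% | √1.031 = 1.016 | √1.070 = 1.035 | √1.125 = 1.061 |

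The SD therefore grows by 15%, 31% and 51% at s = 25%, by 4%, 9% and 15% at s = 50%, and by 2%, 3% and 6% at s = 80%.

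**Check on the log scale with within-run error included.** Log SD = √ln(1 + CV²). With a within-run CV of 5% to 10% and a between-run CV of 10% to 20%, the ratio of separate-run to same-run SD is 1.09 to 1.35 when the SD of the true log change is 0.3, 1.04 to 1.14 at 0.5, and 1.02 to 1.06 at 0.8. The pattern is the same: the loss matters when true changes are fairly uniform across patients and is small when they vary widely.

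**Drift.** A 10% upward shift between the two runs adds ln(1.10) = 0.095 to that patient's log change. If the same shift affected every patient, adding patients would not reduce it. If it affected only some, the mean would move by 0.095 times their fraction.

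**The case against.** The strongest reply is that this is a small matter in an exploratory analysis whose handling details belong in the laboratory manual. Section 17.5 treats laboratory correlates as hypothesis-generating, and Section 17.3 plans no formal test. The manual may already specify batching, controls and lots. Both points stand: the absence of such detail from the protocol does not show that it is absent from the manual. But the protocol does state when the assay is run. If the manual says otherwise, the two need reconciling.

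A reader might draw three stronger conclusions, and the documents support none of them.

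- **That the trial's stated precision is eroded, or that 18 pairs shrink to some smaller effective number.** The 18 patients, the 0.5 SD and the post-minus-pre score in Section 17.3 concern immune cell frequencies measured by flow cytometry. No interval, estimand or sample size is stated for cytokines. The 25% yardstick in Section 17.3 is likewise given for other markers.
- **That drift must push every patient's change the same way.** That needs drift in one direction throughout the study. Section 1.4.7 spreads enrolment over 18 to 24 months, and Section 17.2 requires 8 weeks of observation after Y90-RE before new patients are treated. One patient's final sample may therefore be run before the next patient's baseline, and a lot change affects only patients whose window spans it. Baselines spread over accrual give a partial check.
- **That flow cytometry has the same fault and remedy.** It is also done at collection, but it is a separate assay that may need fresh cells, and its controls and gating may be set in the manual.

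Batching has its own weakness. Frozen baselines are stored about 10 weeks longer than final samples, so a storage effect would also be ordered pre to post.

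**Conclusion.** The point holds as a modest improvement to a stated method. As written, Section 1.3.1 separates each patient's paired cytokine measurements into different runs about 10 weeks apart. Between-run error is counted twice in every change, and sustained drift or a lot change within a patient's window can bias it.

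The size cannot be taken from the documents. It rests on assumed between-run CVs of 10% to 20% and on how much true changes vary between patients, and it ranges from about 2% to 51% extra SD across the cases shown. Safety assessment, dose escalation, the sample size and the stated precision do not depend on it. The consequence is limited to an exploratory measure that may contribute to the collective immune evaluation described in Section 17.3.

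**What to change.** Replace the timing sentence in the cytokine paragraph of Section 1.3.1 with wording such as: serum is aliquoted and frozen at each visit; after the end-of-treatment visit all of a patient's time points are run on one plate with one reagent lot and a pooled bridging control; each aliquot is thawed once; and run and storage time are recorded. Reconcile the companion laboratory manual with this text.

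The cost is one sentence in the protocol, matching text in the manual, freezer space and a pooled control on each plate. There are two drawbacks. Results arrive after week 8, which delays no protocol decision. Baseline samples are stored about 10 weeks longer than final samples, which is why single thawing and a record of storage time belong in the wording. The change should be made before samples are assayed, because the pairing cannot be recovered later unless spare serum was kept.
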